### **1.j Reporting Procedures**

All serious adverse events will be reported to the HRPO in the following time frames: a) death – immediately; b) life-threatening within 7 calendar days; c) all other SAEs within 15 calendar days using the Electronic Serious Adverse Event Reporting System. Should there be a serious adverse event that occurs that increases the risks to the participants, the study will be stopped, an investigation will be conducted, and a findings report will be generated before the study is resumed.

### **1.k Adverse Event Reporting Period**

The adverse event reporting period will starts from participant enrollment to one-month phone follow-up.

## ***F2 Study Outcome Measurements***

Feasibility outcomes include reach, acceptance, adherence, fidelity, safety, and appropriate efficacy outcome selection are described below. Feasibility outcomes will be assessed by the visit-by-visit grid, rater/interventionist log, the LiFE activity planner, and the feasibility questionnaire.

Reach is defined by recruitment and retention rate. Recruitment rate will be measured by the percentage of residents successfully enrolled in the study. Retention rate will be defined by the percentage of enrolled participants who complete the program. Reach will be documented by OT interventionists in interventionist logs and visit-by-visit grids in REDCap.

Acceptance will be surveyed by the feasibility questionnaire at the last session. The questionnaire contains a question, “Are you satisfied with the Adapted LiFE program?,” using a seven-point Likert scale from one (very unsatisfied) to seven (very satisfied). Follow-up questions will be asked to explore what makes the program satisfying or unsatisfying to the participant.

Adherence will be defined as the average percentage of exercise activities achieved during the intervention period that are recorded in the Adapted LiFE activity planner.

Fidelity will be assessed as the delivery of active and essential ingredients of the program as recorded by OT interventionists in visit-by-visit grids in REDCap. OT interventionists will meet weekly with the principle investigator to review the delivery of essential and active ingredients of Adapted LiFE for quality assurance.

Safety of the program will be evaluated by the number of adverse events documented throughout the study duration. This will be documented by OT interventionists in interventionist logs and visit-by-visit grids in REDCap.

---

The visit-by-visit grid is a checklist of all the elements that the interventionist should cover during each session. The interventionist will fill out the grid after every session is completed.

The rater/interventionist log is a survey that each rater/interventionist need to fill out after each visit to document any adverse event or special notes from a participant.

The LiFE activity planner is a weekly calendar for participants to fill out during the intervention sessions. Participants will record and check off the activities that they have completed.

The feasibility questionnaire consist of open-ended questions for participants and interventionists to review their experience in the study period.

Appropriate efficacy outcome selection are defined as few difficulties to administer questionnaires and assessments for balance, muscle strength and habit formation, which will be the primary and secondary endpoints of future larger trials. The second half of the feasibility questionnaire will also be filled out by the rater/interventionist to review if the questionnaires/assessments are easy to administer or not.

*Balance* will be evaluated to capture the nature of posture control and change of intervention. The literature suggests static balance and dynamic balance are both critical to prevent falls. Static balance will be measured by the Four-Stage Balance Test and the Center of pressure (CoP) path. Dynamic balance will be assessed using the timed tandem walk test, the Short Physical Performance Battery-Balance Test, and the Berg Balance Scale. Balance self-efficacy will be measured by the Activities-specific Balance Confidence Scale.

The Four-Stage Balance Test consists of four progressively more challenging stances (narrow base stand, half tandem stand, tandem stand, and one-leg stand). Each stance represents a different level of static balance ability. It is validated to screen for increased fall risk and functional decline. The inability to hold the fourth stage or one-leg stand for five seconds further predicts injurious falls. Participants will be categorized into low fall risk (passing the third stage tandem stand) or high fall risk (failure to pass the third stage tandem stand). A balance board BTrackS will be used to quantify the trajectory of center of pressure (CoP) while participants are being evaluated with The Four-Stage Balance test along with wide stance. The BTrackS balance board is portable and steady with customized software to evaluate the CoP trajectory of participants.

The Short Physical Performance Battery-Balance Test (SPPB) is an assessment of lower extremity function with three subtests: (1) standing balance, (2) four-meter gait speed, and (3) five repetitions of sit-to-stand motion. Subtest scores are added to obtain a summary score that represents mobility function. The SPPB has been shown to be reliable (intraclass correlation coefficients [ICC]: 0.88-0.92), valid, and sensitive to change.

The Berg Balance Scale (BBS) is a 14-item assessment of static and dynamic balance. Performance quality, time, and assistance required are rated on a scale of 0-4 based on pre-specified criteria. Total scores range from 0-56, with a score of 45 or below indicating high risk of falls. The BBS has excellent test-retest reliability (ICC= 0.91) and intra-rater reliability (ICC = 0.98) as well as good criterion validity. It has 82.5% sensitivity and 93% specificity for predicting falls among older adults.

---

CoP parameters were measured by the Balance Tracking System (BTrackS). BTrackS is operated with a portable balance place, and the BTrackS software. The BTrackS software calculates CoP parameters such as total COP path length (cm) and mean CoP velocity (cm/s). The BTrackS system has good concurrent validity ( $r > 0.9$ ) and test-retest reliability ( $ICC = 0.83$ ) for community dwelling older adults. Participants were instructed to stand on the balance plate and perform 4 quiet standing conditions: (1) hip-width stand, eyes open; (2) hip-width stand, eyes closed; (3) narrow stand, eyes open; (4) narrow stand, eyes closed. For each task, participants were instructed to stand still with hands naturally on the side of the hip. Each task was tested for three 30-second trials in order. Participants could choose to take a break after each trial.

Dynamic balance was assessed using the timed forward tandem walk test over a 3-meter course. The participant was instructed to place one foot in front of the other making sure that, with each step, the heel of one foot was directly in front of the toes of the other foot. The participant was told to walk forward as fast as possible without falling or making any mistakes. The average time recorded to the nearest 0.1 seconds from 2 trials was used in the analysis. In addition to time, the number of mistakes (misplacement of steps) was also recorded.

The Activities-specific Balance Confidence (ABC) Scale is a 16-item assessment of balance confidence. Participant self-reports percentage points on the scale from 0% (no confidence) to 100% (very confident) of performing various ambulatory activities without falling or experience sense of unsteadiness. The final score is an average of the 16 items. The higher the percentage, the more confident a person is. The ABC is internally consistent and demonstrated good test-retest reliability, convergent and criterion validity.

**Muscle Strength.** The literature suggests lower extremity muscle strength is critical in preventing falls. Muscle strength training is a core component of Adapted LiFE. Lower extremity muscle strength will be assessed using a Lafayette 01165 dynamometer. This measure has been selected based on the pilot study to avoid a ceiling effect. The dynamometer is an objective and accurate tool to assess lower extremity muscle strength. A standardized protocol will be used by all raters to guide strength measurements of hip flexion, knee extension, and ankle dorsiflexion using dynamometry. The groups of muscles responsible for these movements are critical for mobility and balance to prevent falls.

**Habit formation,** will be measured using the Self-Reported Habit Index (SRHI). This 12-item assessment incorporates constructs such as habit strength, frequency, relevance to self-identity, and automaticity. Items are self-rated by participants using a seven-point Likert scale. Higher scores indicate that a behavior is more strongly habitual.

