### A1 Study Abstract

The purpose of this study is to pilot test the feasibility of a study design for future larger trial of Adapted LiFE among medically underserved older adults. We will evaluate if : 1) Adapted LiFE is feasible for medically underserved older adults, and 2) the study design is feasible with working randomization module and appropriate measurements.

Feasibility outcome measures include reach, acceptance, adherence, fidelity, safety, and appropriate efficacy outcome selection for balance, lower extremity muscle strength, and habit formation.

We will conduct a pilot RCT with an attentional control group. The treatment (Adapted LiFE) group (n=8) will receive 7-sessions of culturally Adapted LiFE over 12 weeks, while the attentional control group (n=8) will receive the same amount from an interventionist with a gentle flexibility program "Go4life" developed by the National Institute on Aging during intervention period.

We will recruit older adults who: are age 70 or older; self-report falls in the past 12 months; and reside in a medically underserved area. We will exclude participants who: have attention and memory impairment (Short Blessed Test score  $\geq 8$ ), are unable to stand with assistive devices, are severely depressed (The Geriatric Depression Scale  $\geq 10$ ), and have serious health conditions for which exercise is contraindicated. Paired t-tests will be used to test time effects, and independent t-tests will be used to test group effects of Adapted LiFE.

---

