## **C Study Objectives**

### ***C1 Primary Aim***

The primary aim of this study is to establish feasibility of Adapted LiFE and a RCT design.

WE hypothesis that the feasibility pilot study will have high reach (60% recruitment and 80% retention rate of targeted participants), acceptance (80% of participants rating high satisfaction with Adapted LiFE), adherence (80% of all exercise activities achieved during the intervention period for each participant), fidelity (90% consistency of elements delivered by occupational therapists throughout the study period), safety (no adverse events caused by Adapted LiFE), and appropriate efficacy measurement selection (70% of the participants do not show floor/ceiling effects among balance, muscle strength, and habit outcomes at pre- and/or post-tests).

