#### **1.d Post-test**

After the last session, a blinded rater OT interventionist will start the post-test immediately or re-schedule another time if participant is unavailable. A set of questionnaires and assessments similar to pre-test will be administered except the demographic questionnaires. The feasibility questionnaire with open-ended questions will be conducted by the rater to explore participants' perspective of the programs.

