## **G4 Missing Outcome Data**

For feasibility outcomes, all data will be used in the final data analysis. Participants who have missing data will still be included.

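### Acceptance is rated only at the end of the program, with no exit rating and no denominator rule, so in practice the 80% criterion rests on completers and may overstate acceptance

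*Combined protocol and SAP*

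**What the plan says.** C1 lists among the feasibility targets "acceptance (80% of participants rating high satisfaction with Adapted LiFE". It does not say who forms the denominator or which scores on the seven-point scale count as high.

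F2 fixes the timing: "Acceptance will be surveyed by the feasibility questionnaire at the last session". The rating is a single item scored from one to seven. F 1.d assigns the questionnaire to the post-test: "The feasibility questionnaire with open-ended questions will be conducted by the rater", and that visit follows the end of the program: "After the last session, a blinded rater OT interventionist will start the post-test immediately".

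Three other places bear on people who stop early:

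- E2 2.f and 2.g cover the right to withdraw and the storage of data. Neither describes an exit visit or exit questionnaire.
- F 1.i has withdrawn subjects' data deleted and left out of the analysis, apart from the reason for withdrawal and demographics.
- G4 says of the feasibility outcomes that all data are used, and "Participants who have missing data will still be included". It gives no rule for scoring a missing rating.

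The arm is small: "The treatment (Adapted LiFE) group (n=8) will receive 7-sessions". Loss is expected, since C1 aims for "high reach (60% recruitment and 80% retention rate of targeted participants".

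**The concern.** Someone who stops at, say, session 3 of 7 is never asked the satisfaction question. G4 can keep that person in the data set but cannot supply an answer that was not collected. Repairing the deletion rule in F 1.i would not supply it either. Unless the analyst chooses otherwise, the percentage is taken over those who reached the end.

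If early stoppers are less satisfied than completers, that percentage rises as they leave. A primary-aim criterion meant to help decide whether a larger trial is reasonable (B2) could then be met partly because of dropout. The missing ratings cannot be recovered once the study is over.

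**Working it through.** The plan gives no calculation for this criterion (G1 declines one), so there is no figure of its own to reproduce.

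**Inputs from the documents.** Adapted LiFE arm n = 8 (A1); acceptance target 80% (C1); retention target 80% (C1); completion in the single-group pilot 8/9 = 89% (D1).

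**Assumptions, not in the documents.** Completion r = 0.80 (the retention target) or 8/9; proportion of completers highly satisfied s = 0.85; proportion of stoppers who would be highly satisfied d, varied from 0 to 0.85. Participants are treated as independent.

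**Step 1: what meets 80%.** With m completers, the smallest passing number is 0.8m rounded up.

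| Completers | Needed | On completers | Same number over 8 |
|---|---|---|---|
| 8 | 7 | 87.5% | 87.5% |
| 7 | 6 | 85.7% | 75% |
| 6 | 5 | 83.3% | 62.5% |
| 5 | 4 | 80% | 50% |

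Over all 8, at least 7 must be highly satisfied. If 2 stop and their missing ratings count as not high, the maximum is 6/8 = 75%, while completers can still show 6/6 = 100%.

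**Step 2: chance of passing on completers.** Sum over m of P(m completers out of 8; r) × P(at least the needed number satisfied out of m; s). With r = 0.80 and s = 0.85:

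- m = 8: 0.1678 × 0.6572 = 0.110
- m = 7: 0.3355 × 0.7166 = 0.240
- m = 6: 0.2936 × 0.7765 = 0.228
- m = 5: 0.1468 × 0.8352 = 0.123
- m = 4 or fewer: 0.030 in total

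The sum is 0.73.

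**Step 3: chance of passing on all 8, each with a rating.** p = r·s + (1 − r)·d, and P = 8p⁷(1 − p) + p⁸.

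| d | p | P |
|---|---|---|
| 0 | 0.68 + 0.20 × 0 = 0.68 | 0.172 + 0.046 = 0.22 |
| 0.25 | 0.68 + 0.05 = 0.73 | 0.239 + 0.081 = 0.32 |
| 0.50 | 0.68 + 0.10 = 0.78 | 0.309 + 0.137 = 0.45 |
| 0.85 | 0.68 + 0.17 = 0.85 | 0.385 + 0.272 = 0.66 |

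The row d = 0 is also the result when no stopper is rated and a missing rating counts as not high. In the row d = 0.85 stoppers are as satisfied as completers. The remaining difference from 0.73 is then not bias: it comes from the pass mark falling on different whole numbers when the denominator is smaller.

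**Step 4: other completion and satisfaction rates, with d = 0.**

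| Completion | Completers satisfied | On completers | On all 8 |
|---|---|---|---|
| 0.80 | 0.80 | 0.60 | 0.15 |
| 0.80 | 0.90 | 0.85 | 0.30 |
| 8/9 | 0.80 | 0.57 | 0.28 |
| 8/9 | 0.85 | 0.71 | 0.38 |
| 8/9 | 0.90 | 0.84 | 0.50 |

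**Step 5: does the retention criterion catch it?** F2 says "Retention rate will be defined by the percentage of enrolled participants who complete the program", which covers both arms. If 13 of 16 complete (81%), retention is met. If all three losses are in Adapted LiFE, 5 of 8 complete there, and 4 of those 5 rating high gives 80%. Both criteria are met, although only 4 of the 8 people given the program reported high satisfaction.

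**The case against.** The strongest counter-argument is that the plan nowhere says completers are the denominator. C1 speaks of participants, and G4 includes people with missing data. A reader might infer that a completers-only rule is written into the plan. It is not: the denominator is left undefined. What stands is that, with no exit rating and no scoring rule, completers are the only people with an answer.

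A reader might also infer that those who leave are the dissatisfied ones. The documents do not support that. E2 2.f provides for withdrawal after a serious adverse event, illness is another plausible reason in people aged 70 or older who have fallen, and D1 gives no reason for the pilot's one non-completer. The direction of any bias is therefore conditional, and Step 3 shows how far the size depends on it.

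The last session could mean a person's own last attended session. That is the weaker reading: nobody knows in advance that a session will be the last, and F 1.c and I3 tie the end of the program to session 7.

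Scoring a missing rating as not satisfied also makes acceptance partly a second measure of retention. That is a fair objection to using it as the only pass rule, though not to showing it. Reasons for withdrawal are kept under F 1.i, but they are not satisfaction ratings.

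Finally, this is a 16-person descriptive pilot with no go/no-go rule tied to acceptance alone, and nothing goes wrong if everyone in the arm completes. That limits the weight of the point but does not remove it, because the plan's own target tolerates 20% loss.

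**Conclusion.** The concern holds in limited form. Under the plan as written, acceptance will in practice be a completers' figure, and it can overstate acceptance if early stoppers are less satisfied. G4 does not cure this, and the retention criterion covers it only in part.

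On the assumptions of 80% completion and 85% of completers satisfied, the chance of meeting the criterion is 0.73 on completers, against 0.22 to 0.66 on all 8 as stopper satisfaction goes from 0% to 85%. At the pilot's 8/9 completion with no stopper satisfied it is 0.71 against 0.38. The contrast of 0.73 with 0.22 should not be read as the size of the bias: it is the extreme case in which every stopper counts as not highly satisfied. All these figures also presuppose a cut-point for high satisfaction, which the plan does not give.

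The change is worth making before enrolment because it is cheap and cannot be made afterwards.

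**What to change.** 1. In F2 and F 1.d, ask the same seven-point item once, by phone or at exit, of anyone who stops Adapted LiFE early and is willing to answer.
2. Amend F 1.i so that this rating is kept and analysed, consistent with G4. Without this change the deletion rule would remove the exit rating.
3. In C1 and F2, report acceptance over all participants randomized to Adapted LiFE. State the number unrated, show the result with unrated counted as not highly satisfied, and put the completers-only percentage beside it. Call the 80% criterion robustly met only if both figures reach it.
4. In the same sentence, state which scores count as high satisfaction, since no percentage can be judged without that.

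The cost is one exit question and short edits to C1, F2, F 1.d and F 1.i. No extra participants are needed and the intervention does not change. The figure over all randomized may be less favourable, and it will be conservative when people leave for reasons unrelated to the program.

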At the second phase, a single-group pilot study was conducted to test the feasibility of Adapted LiFE (Figure 1). Feasibility outcomes were selected based on the Reach, Efficacy, Adoption, Implementation, and Maintenance (RE-AIM) framework to evaluate initial Adapted LiFE (Table 1). Eight medically underserved older adults were recruited by convenience sampling from one senior apartment building in a health provider shortage area. Inclusion criteria were: (1) age 60 or older; (2) living independently; and (3) self-reported a slip, trip or fall in the past 12 months or were "concerned or worried about falling in the future." Exclusion criteria were: (1) Short Blessed Test score  $\geq 10$ , indicating cognitive impairment consistent with dementia; (2) inability to stand independently with a walking device; and (3) a serious health condition for which exercise is contraindicated. Participants were recruited through flyers and information sessions held in the senior apartment building. After consent, an occupational therapist would conduct a pre-test of preliminary efficacy outcomes and then start the first session of Adapted LiFE. Once participants completed all 7 sessions, a post-test was conducted by the OT immediately after the last in-home intervention session. The result showed that Adapted LiFE demonstrated good feasibility among the target participants. Eight older adults completed the pilot study (mean age  $66.4 \pm 5.6$ , 4 males, 3 African Americans, 5 Caucasians). The recruitment rate was 44% (11 enrolled out of 25 screened). The retention rate was 89% (8 completed out of 9 enrolled). Participants had high acceptance of adapted LiFE with a mean satisfaction score of  $6.89 \pm 0.38$ . The average adherence rate was 81.3%. For fidelity, 98% of components were delivered during the intervention period.

Thus, we regard the Adapted LiFE has the potential to have high acceptance and adherence rate among medically underserved older adults. Future studies should aim to evaluated the efficacy of Adpated LiFE with larger trials.

Figure 1 Overview of single group pilot study

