### **3.b Control: Go4life**

Participants in the attention control group will receive a gentle exercise intervention that consists of flexibility activities. Materials are modified from the Go4Life program (an online material developed for general older adults by National Instituted of Aging).

Participants will learn 19 gentle stretching activities during a 12 week intervention period. The OT practitioner will teach participants to gently stretch neck, shoulder, upper arm, upper body, chest, back, foot, leg, and hip. The OT practitioner will not actively guide or request participants to set goals or record activities.

The dose (visits and time) of the attention control intervention is the same as Adapted LiFE, which consists of five weekly sessions and two booster sessions. Each session will last 40-60 minutes. Nineteen gentle flexibility activities from Go4Life will be taught to participants. The OT interventionist will deliver the Go4Life user manual to the participant during the first visit and serve as a consultant for participants to ask questions about the flexibility activities. The self-monitoring calendar will be removed because self-monitoring is an active ingredient of the treatment effect of Adapted LiFE. The OT interventionist will not actively guide or request participants to set goals or record activities. feasibility outcome such as enrollment status, fidelity of intervention delivery will be documented by rater/interventionist log throughout the study period.

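### F2 does not evaluate C1's floor/ceiling benchmark, section 1.i excludes withdrawn participants' data that G4 would use, and the recruitment denominator is unsettled; adherence needs only clarification

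*Combined protocol and SAP*

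**What the plan says.** **Measure selection.** C1 Primary Aim sets the target: "70% of the participants do not show floor/ceiling effects among balance, muscle strength, and habit outcomes at pre- and/or post-tests". F2 Study Outcome Measurements describes the same outcome differently: "Appropriate efficacy outcome selection are defined as few difficulties to administer questionnaires and assessments". The rater or interventionist judges this on the feasibility questionnaire, and F2 gives no threshold. F2 mentions a ceiling only to justify the dynamometer: "This measure has been selected based on the pilot study to avoid a ceiling effect".

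**Withdrawn participants.** Section 1.i (Data Collection Procedures for Adverse Events) removes a withdrawn participant's data from the database and the analysis, apart from the reason for leaving and demographics. G4 Missing Outcome Data has all feasibility data analysed and retains participants with gaps. Section 2.g says that the information stays in REDCap until the study ends.

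**Recruitment.** C1 asks for "high reach (60% recruitment and 80% retention rate of targeted participants". F2 takes residents as the denominator. D1 Preclinical Data, on the earlier single-group pilot, used people screened. Section 2.a makes referrals a main channel, and section 2.c adds controls from a previous study.

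**Adherence.** C1 has "adherence (80% of all exercise activities achieved during the intervention period for each participant", and F2 has "Adherence will be defined as the average percentage of exercise activities achieved during the intervention period", taken from the activity planner. D1 reported the earlier pilot as an average ("The average adherence rate was 81.3" per cent). Only the Adapted LiFE arm (n=8) has this record; section 3.b explains: "The self-monitoring calendar will be removed because self-monitoring is an active ingredient of the treatment effect of Adapted LiFE".

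**The concern.** The primary aim is to establish feasibility, so these criteria are what the pilot delivers. G2 plans only descriptive statistics, and B2 says the results will help decide whether the main study is reasonable. Where F2 measures something other than what C1 benchmarks, or where two sections disagree on whose data count, the verdict depends on the section the analyst follows. That choice could then be made after the results are known.

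Two consequences stand out. A measure that is easy to administer but sits at its ceiling would satisfy F2 and be carried into the main trial, although C1 was written to screen it out. And if people who adhere poorly are more likely to withdraw, leaving them out raises reported adherence.

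**Working it through.** **1. Measure selection.** C1 concerns the distribution of participants' scores at pre-test and post-test. F2 concerns the assessors' experience of giving the tests. One cannot be calculated from the other, so F2 as written does not evaluate the 70% benchmark.

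C1's own wording on timing is also open. Suppose, for one instrument, 3 of 16 participants are at ceiling at T1 and 3 different participants at T2 (assumed):
- free at each visit: (16 − 3)/16 = 81.25%, above 70%;
- free at both visits: (16 − 3 − 3)/16 = 62.5%, below 70%.

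The same data pass or fail according to how the and/or is read.

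**2. Withdrawn participants.** Inputs: eight in the Adapted LiFE arm (Study Abstract) and the 80% benchmark (C1). Assumptions: completers average 85%, and the withdrawn participant has the value shown. With exclusion, adherence is 85% in every row.

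| Withdrawn (assumed) | Adherence with data kept | Crosses 80%? |
|---|---|---|
| one at 40% | (7×85 + 40)/8 = 79.4% | yes |
| one at 60% | (7×85 + 60)/8 = 81.9% | no |
| two at 60% | (6×85 + 2×60)/8 = 78.75% | yes |
| two at 40% | (6×85 + 2×40)/8 = 73.75% | yes |

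For a single withdrawal the break-even value is 8×80 − 7×85 = 45%; below that, exclusion changes the verdict. Retention would not necessarily flag the problem: two withdrawals here and one in the control arm give 13/16 = 81.25%, still within C1's 80%.

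**3. Recruitment.** The earlier pilot's figures reproduce: 11/25 = 44% and 8/9 = 88.9%, printed as 89%. The denominator of the first is people screened, which is neither of the terms in C1 and F2. With 16 enrolled, 60% requires a denominator of at most 26 (16/26 = 61.5%; 16/27 = 59.3%). At 36 the rate is 44.4%. The number of residents is not stated; assumed values of 50, 100 and 200 would give 32%, 16% and 8%. People referred, or identified from the previous study, need not be residents, so they could enter the numerator without being in the denominator.

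**4. Adherence.** If C1 means a percentage calculated for each person, F2 simply averages those percentages and the two sections agree. They conflict only if C1 requires every participant to reach 80%. Under that reading, seven at 90% and one at 20% average (7×90 + 20)/8 = 81.25%, so the mean meets 80% while one person does not.

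To see how demanding that reading is, I take a true mean of 81.3% (D1), n=8, a beta distribution and assumed between-person SDs of 5, 10 and 15 points (1,000,000 simulated trials each). The mean reaches 80% in 77%, 66% and 62% of trials. All eight reach it in 2.4%, 1.8% and 2.1%.

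**The case against.** **Adherence.** A reader might infer that C1 and F2 impose opposite adherence rules. The documents do not establish that. Where C1 wants a share of participants it says so, as it does for satisfaction and for floor/ceiling effects. F2 has no adherence threshold of its own, and the earlier pilot reported an average. An all-eight rule that would pass about 2% of the time at that pilot's mean is an unlikely target. This objection stands, and it reduces adherence to a clarification. Having the planner in one arm only is a deliberate choice with a stated reason.

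**Withdrawn data.** A reader might also infer from section 2.g that the data are both kept and deleted. Section 2.g is about storage and can be reconciled with later deletion. G4 is about missing data and does not name withdrawn participants, and section 1.i sits among the adverse-event procedures, so its reach to other withdrawals is unclear. Those limits are fair. What remains is that section 1.i takes data out of the analysis while G4 says all feasibility data go in.

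**Recruitment.** Two senior buildings are a recruitment site, so residents is not an arbitrary term. It is incomplete, because other routes are planned. Nothing ties the 60% to enrolled over screened, however; C1's wording could equally mean eligible people. The earlier pilot counted 11 enrolled for recruitment and 9 for retention (8/11 would be 73%). That concerns how a finished study was reported and is not a result of this plan. It shows only why the term needs fixing here.

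**Weight.** The pilot is small, descriptive and without hypothesis tests, and most individual values could be reported under either definition. That does not help with data that have been deleted, or with a floor/ceiling analysis that F2 never specifies.

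**Conclusion.** The point holds, and the plan should be amended. Two parts are firm. F2 does not evaluate C1's 70% floor/ceiling criterion. Section 1.i's exclusion conflicts with G4's use of all feasibility data, and it can bias adherence upward if poor adherers withdraw. In the single-withdrawal examples the reported figure rises by 5.6 points (85 − 79.4) or 3.1 points (85 − 81.9), and only the first crosses 80%. The completer mean, the number of withdrawals and the withdrawn values are all assumed, because the documents give none.

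The recruitment denominator is inconsistent across C1, F2 and the earlier pilot, and F2's version does not cover all planned sources. Adherence needs a clarifying sentence and no more.

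C1's percentages are benchmarks. A reader might take them as a formal go/no-go rule, but no section makes them one; B2 says only that the results will inform the decision.

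**What to change.** 1. **Measure selection (F2, with C1's timing wording).** Apply the 70% floor/ceiling rule to each instrument, at T1 and at T2 separately. Report ease of administration as a separate descriptive item.
2. **Withdrawn participants (section 1.i).** Amend it so that feasibility data collected before withdrawal are kept and analysed, in line with G4 and subject to the consent wording. State whether the rule covers all withdrawals or only those after an adverse event.
3. **Recruitment (C1 and F2).** Use one denominator that covers every source, and have the sponsor state which denominator the 60% refers to. Report both enrolled/screened and enrolled/eligible from the screening log, and use one count of enrolled for recruitment and retention.
4. **Adherence (C1 and F2).** State that each participant's percentage is averaged over all those randomised to Adapted LiFE and compared with 80%. Also report how many individually reach 80%.

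The cost is a wording amendment and a check of the consent form. The planner records and screening log are already planned, so no visit or assessment is added. The downside is that reported adherence may be lower, possibly below 80%, once withdrawn participants are included.
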